**Table 8-1 Logic for Determining the Category of a Medication**

Medication start date	Medication end date				
	< Start date of TE Period 1	≥ Start date of TE Period 1 and ≤ End date of TE Period 1	> End date of TE Period 1 and < Start date of TE Period 2	≥ Start date of TE Period 2 and ≤ End date of TE Period 2	> End date of TE Period 2
< Start date of TE Period 1	P	PC1	PC1A	PC1C2A	PC1C2A
≥ Start date of TE Period 1 and ≤ End date of TE Period 1	-	C1	C1A	C1C2A	C1C2A
> End date of TE Period 1 and < Start date of TE Period 2	-	-	A	C2A	C2A
≥ Start date of TE Period 2 and ≤ End date of TE Period 2	-	-	-	C2	C2A
> End date of TE Period 2	-	-	-	-	A

P – Prior; C1 – Concomitant for the Treatment in Period1; C2 – Concomitant for the Treatment in Period 2; A – Post-Treatment.

## 8.2.5 Study Drug Exposure

Exposure summaries will be based on the FAS and presented by treatment group.

Duration of study drug exposure is defined as follows: last dose date – first dose date + 1 day within the treatment period, regardless of any interruption in dosing between the first and the last dose.

Duration of study drug exposure expressed in weeks will be summarized descriptively (number, mean, SD, median, minimum, and maximum) and also into the following categories:  $\leq 2$  weeks,  $> 2 - \leq 4$  weeks,  $> 4 - \leq 8$  weeks,  $> 8$  weeks. Additionally, the total duration of study drug exposure, defined as the total of duration of study drug exposure of all subjects and expressed in patient years, will be provided.

## 8.2.6 Study Drug Compliance

Study drug compliance will be measured by the compliance rate; summarized based on the FAS and presented by treatment group.

Compliance rate will be calculated as follows:

$$100 \times [1 - (\text{Total number of days study drug interrupted}) / (\text{Duration of study drug exposure})].$$

The total number of days study drug interrupted is defined as the total of number of days the study drug was interrupted in each interruption interval; where number of days study drug interrupted in each interval is defined as the interruption end date - the corresponding interruption start date + 1.

The Compliance rate will be summarized descriptively by the number of subjects (n), mean, SD, median, min, and max and into the categories of  $< 80\%$  or  $\geq 80\%$ .

A list of subjects with  $< 80\%$  compliance rate will be provided.

## 8.2.7 Important Protocol Deviations

Important protocol deviations (IPD) are a subset of protocol deviations that may significantly impact the completeness, accuracy, and/or reliability of the study data or that may significantly affect a subject's rights, safety, or well-being. IPD rules will be developed and finalized before database lock.

The protocol deviations that should be considered as potential IPDs include, but are not limited to:

- Violation of subjects rights, safety or well-being
- Subject entered the study despite violation of any inclusion or exclusion criteria
- Subject was less than 80% compliant with study medications
- Subject received excluded concomitant medications

- Subject received the wrong treatment or incorrect doses
- Subject remained in study despite meeting withdrawal criteria

Occurrence of any of these events should be considered as potential IPDs, but the blinded team should categorize them as IPDs only if they have the potential to affect interpretation of study results.

IPDs (from the clinical database or from the site deviation log) will be summarized descriptively based on the FAS and presented by treatment sequence. Additionally, IPDs will be provided as a subject data listing.

### **8.3 Efficacy Analysis**

The primary objective of this study is to evaluate the efficacy of TEZ/IVA and IVA monotherapy. For efficacy analysis, the statistical inference will be based on change from study baseline. Unless otherwise defined, all efficacy analyses described in this section will use the FAS. The efficacy analyses will be performed according to the treatment to which the subject was assigned in each period. Data for a period will be used provided that the subject received at least one dose of study drug in that treatment period.

#### **8.3.1 Analysis of Primary Efficacy Endpoint**

The analysis will include all available measurements up to Week 8 [inclusive] during each treatment period, both on-treatment measurements and measurements after treatment discontinuation, per the visit windowing rules (Section 8.1).

##### **8.3.1.1 Definition of Primary Efficacy Endpoint**

The primary efficacy endpoint is the absolute change in ppFEV1 from study baseline to the average of the Week 4 and Week 8 measurements in each of the two Treatment Periods.

ppFEV1 is the ratio of FEV1 (L) to the predicted FEV1 (L), expressed as a percentage. The predicted FEV1 will be calculated using the Hankinson and Wang standards; details are in Section 10.3.

##### **8.3.1.2 Primary Analysis of Primary Efficacy Endpoint**

The primary efficacy analysis will be based on a mixed effects model using SAS procedure MIXED. The null hypotheses to be tested are that the mean absolute change from study baseline in ppFEV1 to the average of the Week 4 and Week 8 measurements is the same for (i) TEZ/IVA and placebo and (ii) IVA monotherapy and placebo.

The primary analysis model will include the absolute change from study baseline in ppFEV1 to the average of the Week 4 and Week 8 measurements as the dependent variable and the following fixed effects: treatment, period, ppFEV1 at study baseline, and subject as a random effect. The within-subject covariance will be assumed to have the same compound symmetry (CS) structure for sequences containing placebo treatment but will be different from the CS structure for sequences containing active treatment in both periods. Denominator degrees of

freedom for the F-test for fixed effects will be estimated using the Kenward-Roger approximation. The estimated mean of the dependent variable, a 95% confidence interval, and a 2-sided *P* value will be provided for each treatment. Similarly, the estimated between group treatment differences along with the corresponding 95% CI and 2-sided *P* values will be presented.

No imputation of missing data will be performed. Subjects who have data only for one of the periods will have a data structure similar to a parallel-group trial. Assuming that these subjects have dropped out at random, an estimate of treatment effect based on such subjects will be combined with the estimate from subjects who have data in both treatment periods with weights based on the precision of these estimates.

The drop-out rate is expected to be low based on the experience with other CF studies (for example, drop-out rate in Study VX12-809-103 was 4.6%, Study VX12-809-104 was 5.2% and Study VX12-770-111, a crossover study, was 7.7%). Note that carryover effects are not included in the model; such effects are not expected because of the long washout period.

The SAS code to implement the primary analysis will be similar to the code presented below:

```
proc mixed data=xxx;
  class subject period treatment group;
  model primary efficacy endpoint = period treatment
        ppFEV1 at study baseline/ddfm=KR;
  repeated period/sub=subject type=cs group=group;
  lsmeans treatment / pdiff cl;
run;
```

where “primary efficacy endpoint” is the average absolute change from study baseline in ppFEV1 at weeks 4 and 8 in each treatment period. The Group= statement will specify the variable so that the covariance structure will be different for each value of the variable.

Descriptive statistics associated with the raw value and the absolute change from study baseline in ppFEV1 at post-baseline visits (Day 15, Weeks 4, and 8) along with the average ppFEV1 at Weeks 4 and 8 and the average absolute change from study baseline in ppFEV1 at Weeks 4 and 8 will be summarized by treatment group. Subjects with missing ppFEV1 at both Week 4 and Week 8 visits will have missing average ppFEV1 at Weeks 4 and 8. Therefore, they will not be included in the related summaries. The cumulative distribution of the average absolute change from study baseline in ppFEV1 at Weeks 4 and 8 in each treatment period will be plotted by treatment group.

In addition, analysis based on an ANCOVA model using absolute change from study baseline in ppFEV1 to the average of the Week 4 and Week 8 measurements from Treatment Period 1 will be performed to assess the treatment effect difference in case there is a carryover effect. The resulting model will include treatment, age group at screening (<18 vs. ≥18 years old), ppFEV1 at study baseline and category of residual function mutation (Class V non-canonical splice mutation versus Classes II to IV residual function mutation). The estimated mean of the dependent variable for each treatment and between treatment differences will be presented along with the 95% CI.

[REDACTED]

### 8.3.2 Analysis of Secondary Efficacy Endpoints

The following is a key secondary efficacy endpoint:

1. Absolute change in Cystic Fibrosis Questionnaire-Revised (CFQ-R) respiratory domain score from study baseline to the average of the Week 4 and Week 8 measurements in each Treatment Period

The study also has the following other secondary efficacy endpoints:

2. Relative change in ppFEV1 from study baseline to the average of the Week 4 and Week 8 measurements in each Treatment Period
3. Absolute change in sweat chloride from study baseline to the average of the Week 4 and Week 8 measurements in each Treatment Period

#### 8.3.2.1 Definition of Secondary Efficacy Endpoints

##### 8.3.2.1.1 Key Secondary Efficacy Endpoint

###### **Absolute Change in CFQ-R respiratory domain score from study baseline to the average of the Week 4 and Week 8 measurements in each Treatment Period**

The absolute change from study baseline in the respiratory domain of the CFQ-R (Pooled 'Children Ages 12 and 13' Version and 'Adolescents and Adults' Version) to the average of Week 4 and Week 8 measurements in each treatment period will be analyzed based on the *CFQ-R scaled scores* described below.

The CFQ-R is a validated CF-specific instrument that measures quality-of-life domains. This study uses three different versions of CFQ-R forms:

- CFQ-R for Children Ages 12 and 13 has a total of 35 questions to form 8 domains. All questions are scored 1, 2, 3, or 4.
- CFQ-R for Adolescents and Adult (subjects 14 years and older) has a total of 50 questions to form 12 domains. Question 43, which is scored 1, 2, 3, 4, or 5, is not used in calculating any domain; all the other 49 questions are scored 1, 2, 3, or 4.
- CFQ-R for Parents/Caregivers (subjects 13 years and younger) has a total of 44 questions to form 11 domains. Question 37, which is scored 1, 2, 3, 4, or 5, is not used in calculating any domains; all the other 43 questions are scored 1, 2, 3, or 4.

For all three CFQ-R versions, to calculate the score for each domain, the response scores on the negatively phrased questions are reversed (reversed scores = 5 – response scores) so that 1 always represents the worst condition and 4 always represents the best condition.

The scaled score for each domain ranges from 0 (worst condition) to 100 (best condition). It is calculated as follows:

$$\text{Scaled score for a domain} = 100 \times (\text{mean}(\text{scores of all questions in that domain}) - 1)/3$$

The scaled score for a specific domain will not be calculated if more than half of the questions in the domain have missing scores.

Table 8-2, Table 8-3, and Table 8-4 provide the questions included in each domain, the questions with the reversed scores, as well as the maximum number of missing questions for the CFQ-R for Children Ages 12 and 13, the CFQ-R for Adolescents and Adults, and the CFQ-R for Parents/Caregivers respectively. The CFQ-R scoring manual is also provided in Section 10.4.

**Table 8-2 CFQ-R for Children Ages 12 and 13**

Domain	Questions		Reversed questions	Maximum number of missing questions
	Total	Individual		
Physical	6	1, 2, 3, 4, 5, 6	1, 2, 3, 4, 5	3
Emotion	8	7, 8, 9, 10, 11, 12, 13, 14	14	4
Social	7	20, 21, 22, 23, 24, 25, 26	20, 22, 24, 26	3
Body	3	27, 28, 29	-	1
Eat	3	15, 17, 19	19	1
Treatment burden	3	16, 18, 30	18	1
Respiration	4	31, 32, 33, 34	-	2
Digestion	1	35	-	0

**Table 8-3 CFQ-R for Adolescents and Adults (subjects 14 years and older)**

Domain	Questions			Maximum number of missing questions
	Total	Individual	Reversed questions	
Physical	8	1, 2, 3, 4, 5, 13, 19, 20	13	4
Role	4	35, 36, 37, 38	35	2
Vitality	4	6, 9, 10, 11	6, 10	2
Emotion	5	7, 8, 12, 31, 33	-	2
Social	6	22, 23, 27, 28, 29, 30	23, 28, 30	3
Body	3	24, 25, 26	-	1
Eat	3	14, 21, 50	-	1
Treatment burden	3	15, 16, 17	15, 17	1
Health perceptions	3	18, 32, 34	18, 32, 34	1
Weight	1	39	-	0
Respiration*	6	40, 41, 42, 44, 45, 46	43	3
Digestion	3	47, 48, 49	-	1

\*: Question 43 not used to calculate a domain.

**Table 8-4 CFQ-R for Parents/Caregivers (subjects 13 years and younger)**

Domain	Questions			Maximum number of missing questions
	Total	Individual	Reversed questions	
Physical	9	1, 2, 3, 4, 5, 13, 14, 15, 16	15	4
Vitality	5	8, 9, 10, 11, 12	10, 12	2
Emotion	5	6, 7, 23, 25, 26	6	2
School	3	27, 28, 29	28	1
Body	3	19, 20, 21	-	1
Eat	2	17, 44	-	0
Treatment burden	3	18, 30, 31	31	1
Health perceptions	3	22, 24, 32	22, 24, 32	1
Weight	1	33	-	0
Respiration*	6	34, 35, 36, 38, 39, 40	37	3
Digestion	3	41, 42, 43	-	1

\*: Question 37 not used to calculate a domain.

### 8.3.2.1.2 Other Secondary Efficacy Endpoints

#### **Relative change in ppFEV1 from study baseline to the average of the Week 4 and Week 8 measurements in each Treatment Period**

The calculations of ppFEV1 and the relative change from study baseline will follow the definitions in Section 8.3.1.1 and Section 8.1.

#### **Absolute change in sweat chloride from study baseline to the average of the Week 4 and Week 8 measurements in each Treatment Period**

Sweat chloride will be collected at baseline and 2 post-baseline time points (Weeks 4 and 8) in each treatment period. Values > 160 mmol/L or < 10 mmol/L will be set to missing and excluded from the analysis.

Absolute change from study baseline in sweat chloride will be calculated as  $mean(SW_{Left}, SW_{Right}) - SW_{Base}$ , where  $SW_{Left}$  and  $SW_{Right}$  are the measurements obtained on the left and right arms, respectively, at a particular visit and  $SW_{base}$  is the mean of right and left baseline measurements. If one of the two measurements at a time point is missing, the other will be used as the mean.

Note: A volume of  $\geq 15$   $\mu$ L is required for an accurate determination of sweat chloride. Any results reported as having volume <15  $\mu$ L or “Quantity Not Sufficient” (QNS) will be considered missing.

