9.1 Inclusion Criteria

Subjects who meet all of the following inclusion criteria will be eligible:

1. Subject (or their legally appointed and authorized representative) will sign and date an informed consent form (ICF) and, where appropriate, an assent form.
2. Willing and able to comply with scheduled visits, treatment plan, study restrictions, laboratory tests, contraceptive guidelines, and other study procedures.
3. Subjects (males and females) will be aged 12 years or older on the date of informed consent or, where appropriate, assent.
4. Heterozygous for *F508del-CFTR* and a second allele with a *CFTR* mutation predicted to have residual function (see [Section 16](#)). The results of the confirmatory genotype sample obtained during screening must be reviewed before randomization. *CFTR* mutations that are predicted to have residual function were defined using the parameters in [Section 16](#).
5. $FEV_1 \geq 40\%$ and $\leq 90\%$ of predicted normal for age, sex, and height (equations of Wang et al. or Hankinson et al.)^{43,44} during screening. Spirometry measurements must meet ATS/ERS criteria²⁹ for acceptability and repeatability ([Section 8.1.1.1](#)).

Subjects must meet Inclusion Criterion 6 or 7.

6. Sweat chloride value ≥ 60 mmol/L from test results obtained during screening OR as documented in the subject's medical record.
7. If the sweat chloride value is < 60 mmol/L, there must be documented evidence of chronic sinopulmonary disease⁴⁵ manifested by (but not limited to) at least 1 of the following:
 - o Persistent colonization/infection with typical CF pathogens, including *Staphylococcus aureus*, *Haemophilus influenzae*, and mucoid and nonmucoid *Pseudomonas aeruginosa*
 - o Chronic cough and sputum production
 - o Persistent chest radiograph abnormalities (e.g., bronchiectasis, atelectasis, infiltrates, hyperinflation)
 - o Nasal polyps, chronic sinusitis; radiographic or computed tomographic abnormalities of the paranasal sinuses

Specific criteria for such subjects must be discussed with and approved by the Medical Monitor prior to randomization.

8. Stable CF disease as judged by the investigator.
9. Willing to remain on a stable CF medication regimen through Week 24 or, if applicable, the Safety Follow-up Visit.

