11.6.2 Sweat Chloride Testing

The sweat chloride test is a standard diagnostic tool for CF, serving as a biomarker of CFTR activity. Collection of sweat samples will be performed at visits specified in [Table 3-1](#) and [Table 3-2](#), using an approved collection device. Sweat samples will be sent to a central laboratory for testing and interpretation of results. Individual sweat chloride test results will not be disclosed to the study sites. Specific instructions for collection, handling, processing, and shipping of sweat chloride samples to the central laboratory will be provided separately.

The sweat collection on dosing visits should occur approximately 1 hour before the PK sample collection and before the morning dose of the study drugs. At each time point, 2 samples will be collected, 1 from each arm (left and right).

Sweat collection must be performed at the Screening Visit if the sweat chloride value is not available in the subject's medical record. For subjects using a sweat chloride value documented in their medical record to establish eligibility, the sweat chloride test at the Screening Visit is optional. Collection of sweat chloride will not overlap with any other study assessments.

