12.3.3.2 Analysis of Secondary Efficacy Variables

For all secondary efficacy endpoints, the primary analysis will be based on change from study baseline.

Key Secondary Endpoint

- **Absolute change in the CFQ-R respiratory domain score from study baseline to the average of the Week 4 and Week 8 measurements in each Treatment Period:**
Analysis of this variable will be similar to that of the primary analysis of the primary efficacy endpoint.

Secondary Endpoints

[figure not shown]
- **Relative change in percent predicted FEV₁ from study baseline to the average of the Week 4 and Week 8 measurements of each of the Treatment Periods:** Analysis of this variable will be similar to that of the primary analysis of the primary efficacy endpoint.
- **Absolute change in sweat chloride from study baseline to the average of the Week 4 and Week 8 measurements in each Treatment Period:** Analysis of this variable will be similar to that of the primary analysis of the primary efficacy endpoint.

Sensitivity analysis, supportive analysis, and subgroup analysis of secondary variables may be described in the SAP.

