#### **Absolute change in sweat chloride from study baseline to the average of the Week 4 and Week 8 measurements in each Treatment Period**

Analysis of this variable will be similar to the primary analysis of the primary efficacy endpoint. However, ppFEV1 at study baseline will be replaced by sweat chloride at study baseline in the model.

The estimated mean of absolute change from study baseline in sweat chloride to the average of Week 4 and Week 8 measurements will be presented along with the 95% CI and the 2-sided *P* value. Similarly, the estimated differences between treatment groups and the associated 95% CI and *P* value will be presented.

In addition, raw value and absolute change from study baseline in sweat chloride at post-baseline visits (Weeks 4 and 8) along with the average sweat chloride at Weeks 4 and 8 and the average absolute change from study baseline in sweat chloride at Weeks 4 and 8 will be summarized by treatment group using descriptive statistics. The cumulative distribution plot will not be created for this endpoint.

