### 8.3.2.5 Sensitivity, Supportive, and Subgroup Analysis of Secondary Endpoints

No sensitivity, supportive, or subgroup analysis are planned for the secondary endpoints.

[REDACTED]

[REDACTED]

[REDACTED]

[REDACTED]

[REDACTED]

[REDACTED]

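### Does setting sweat chloride readings below 10 or above 160 mmol/L to missing distort the treatment comparison enough to need a change?

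*SAP*

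**What the plan says.** SAP 8.3.2.1.2, on the sweat chloride endpoint: "Values > 160 mmol/L or < 10 mmol/L will be set to missing and excluded from the analysis". Two samples are taken at each time point, one per arm, and "If one of the two measurements at a time point is missing, the other will be used as the mean". A separate note in the same section treats samples under 15 microlitres, or reported as insufficient quantity, as missing. Only that note gives a reason, which is accuracy of the determination.

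SAP 8.3.2.4 analyses the endpoint with the primary mixed model, using baseline sweat chloride as covariate, and reports estimates, 95% confidence intervals and P values. Values by visit "will be summarized by treatment group using descriptive statistics". On further checks, SAP 8.3.2.5 says: "No sensitivity, supportive, or subgroup analysis are planned for the secondary endpoints". The protocol had left this open in 12.3.3.2: "Sensitivity analysis, supportive analysis, and subgroup analysis of secondary variables may be described in the SAP".

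Three other places bear on the point. Protocol 11.6.2 says "Sweat samples will be sent to a central laboratory for testing and interpretation of results". SAP 8.1 lists all individual data and rules out outlier remedies except where specified. SAP 6.4.1 has a treatment-blinded group outside the study team review the sweat chloride data before lock.

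**The concern.** A reading that passes the volume check is still discarded if its value is extreme. Sweat chloride was chosen to show the drugs' effect on CFTR activity, and low values are expected in some subjects, since the entry criteria allow them: "If the sweat chloride value is < 60 mmol/L, there must be documented evidence of chronic sinopulmonary disease". If active treatment lowers chloride, readings under 10 should arise mostly on active drug and readings over 160 relatively more often on placebo. Deleting both trims the two groups from opposite ends, and the missingness depends on the unobserved value.

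The model's stated assumption, "Assuming that these subjects have dropped out at random", does not describe such deletions. The planned tables would show them only in part: if one arm's reading goes, the other stands in and n is unchanged, and the remaining losses are mixed with volume failures. At stake are the point estimate, interval and P value for the pharmacodynamic endpoint. The primary and key secondary tests are not involved.

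**Working it through.** **Inputs.** From the documents: limits 10 and 160; two arms; two visits per period (Weeks 4 and 8); six sequences of 34. The documents state no sweat chloride mean, SD or effect, so there is no plan figure to reproduce, and those inputs are assumed below.

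**Readings at risk.** Each treatment appears in 4 sequences: 4 × 34 = 136 periods, and 136 × 2 visits × 2 arms = 544 readings. The two active treatments together have 1088.

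**Step 1: crude bound.** Treat single readings as normal with mean μ and SD σ. Deleting outside the limits shifts the mean by σ[φ(a) − φ(b)] / [Φ(b) − Φ(a)], with a = (10 − μ)/σ and b = (160 − μ)/σ.

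- Active, μ = 60, σ = 25: a = −2, b = 4; shift = 25 × (0.05399 − 0.00013)/0.97722 = 1.38.
- Placebo, μ = 70, σ = 25: a = −2.4, b = 3.6; shift = 25 × (0.02239 − 0.00061)/0.99164 = 0.55.
- Difference: −10 + 1.38 − 0.55 = −9.17, or 8.3% smaller. With SD 20 it is −9.74, with SD 30 −8.44.
- Letting the other arm stand in (arm correlation 0.9, SD 25) cuts the shifts to 0.985 and 0.368: −10 + 0.985 − 0.368 = −9.38, or 6.2% smaller.

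This bound uses raw values at one visit. The plan analyses change from baseline, adjusts for baseline, compares within subjects and averages two visits. A subject who always reads low then tends to drop out of both sides of the comparison, so the bound overstates the effect in this case.

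**Step 2: the planned analysis, simulated.** Six sequences, left and right arms, the two-group compound symmetry model with period and baseline. Assumed: gamma untreated level with mean 70 and SD 25; effect −10 varying between subjects (SD 8); treated level floored at 2 mmol/L; visit noise CV 15%; arm noise CV 8%.

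| Limit | Active (of 1088) | Placebo (of 544) |
|---|---|---|
| < 10 | about 11 | about 0 |
| > 160 | about 5 | about 4 |

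- Deleted in all: 11 + 0 + 5 + 4 = 20 of 1632 readings, or 1.2%. About 4 of the 20 leave n by visit unchanged.
- Estimate: −10.00 becomes −9.79. The shift of 0.21 is 2.1%, or 0.16 of the standard error with 204 complete subjects.
- A fresh run of this case with three seeds gave 2.0% to 2.1%, or 0.15 to 0.17 standard errors. With one seed, the lower limit alone moved the estimate by 0.13 and the upper alone by 0.09.
- Other forms of effect at the same mean and SD: the same for everyone, 1.1%; proportional to level, 2.1%.
- If a screening value replaces a deleted baseline: 2.5%, against 2.4% on the same seed.

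**Step 3: how far the inputs matter.** Over 72 scenarios (mean 50 to 80, SD 20 to 30, effect −10 or −15, three forms of effect) the estimate ranged from 0.2% larger to 8.6% smaller. At mean 70 it was 0.5% to 4.8% smaller. At mean 50, SD 30, varying effect of −10, the fresh run gave 8.4% smaller with the gamma level but 1.6% larger with a normal level floored at 2. At mean 40, SD 25, it was 10.5% smaller with a varying effect and 4.2% larger with a proportional one. In that last case about 58% of untreated subjects would lie below 40 mmol/L, which protocol 8.2.4 calls normal.

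**Step 4: the cost of keeping extremes.** Suppose one reading is recorded as 250 instead of 70. The period average moves by (250 − 70)/4 = 45, and the treatment mean by 45/136 = 0.33 mmol/L. With model weights at within-subject correlations of 0 to 0.6 the contrast moves by 0.25 to 0.41. That one error exceeds the 0.21 produced by deleting about 20 true readings.

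**The case for a change.** The best argument for a change is that it would cost little. The volume rule already screens for quality, so the range rule also removes readings that pass the SAP's own accuracy condition. Deletion by value is not at random, the direction of its effect cannot be settled from the documents, and the visit counts would hide part of it. A sentence on the limits, a count by treatment and one extra model run would answer the question.

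The factual part stands: no basis is given, and the absence of a sensitivity analysis is explicit. The inference is weaker.

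- A basis may sit in the central laboratory's documents, which are not part of the plan.
- Every percentage above assumes that the deleted readings are true. If they are mostly errors, the rule protects the estimate.
- The at-random sentence concerns subjects with data in one period only. Here a period is lost only when all four readings are missing, about 2 of 272 active periods in the mid-case.
- Individual data are to be listed. If the listings carry results as reported, out-of-range values can be counted by treatment without a new table.
- Even the proposed additions would leave the limits and the main analysis as they are.

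**Conclusion.** No change is needed. The rule trades a small possible bias for protection against gross errors, and retaining the extremes is not clearly better. With mean 70, SD 25 and a difference of −10, the shift is about 1% to 2%, or roughly 0.1 to 0.2 standard errors, toward no difference. This assumes that the deleted readings are real and that the drugs lower chloride. With low means and wide spread it could reach 8% to 10%, and there its sign depends on the assumed distribution and form of effect, so the rule cannot be called conservative in every setting.

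What limits the consequence is where the rule applies. It is to be fixed before lock and unblinding, it is identical across treatments, and it governs an endpoint that SAP 8.3.2.3 leaves outside the testing sequence. No controlled claim depends on it. The missing rationale is a gap in documentation that analysts can fill from the laboratory's records and the listings.
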